7.10.1. Nivolumab Dose Delay/Interruption Criteria

Nivolumab treatment-related interruptions > 6 weeks requires treatment discontinuation (refer to 7.10.3).

Nivolumab administration should be delayed/interrupted according to [Table 8](#):

Table 8: Recommended Treatment Modification for Nivolumab

Immune-related AE	Severity	Treatment Modification
Immune-related pneumonitis	Grade 2 pneumonitis	Withhold nivolumab until symptoms resolve, radiographic abnormalities improve, and management with corticosteroids is complete
	Grade 3 or 4 pneumonitis	Permanently discontinue nivolumab
Immune-related colitis	Grade 2 or 3 diarrhea or colitis	Withhold nivolumab until symptoms resolve and management with corticosteroids, if needed, is complete
	Grade 4 diarrhea or colitis	Permanently discontinue nivolumab
Immune-related hepatitis	AST or ALT ≥ 8 x ULN, OR Total bilirubin ≥ 5 x ULN, OR Concurrent AST or ALT > 3 x ULN and total bilirubin > 2 x ULN	Withhold nivolumab until laboratory values return to baseline and management with corticosteroids, if needed, is complete
	Grade 4 liver enzyme or bilirubin elevation or clinical liver failure	Permanently discontinue nivolumab
Immune-related nephritis and renal dysfunction	Grade 2 or 3 creatinine elevation	Withhold nivolumab until creatinine returns to baseline and management with corticosteroids is complete
	Grade 4 creatinine elevation	Permanently discontinue nivolumab
Immune-related endocrinopathies	Symptomatic endocrinopathies (including hypothyroidism, hyperthyroidism, hypophysitis, adrenal insufficiency and diabetes)	Withhold nivolumab until symptoms resolve and management with corticosteroids (if needed for symptoms of acute inflammation) is complete. Nivolumab should be continued in the presence of hormone replacement therapy as long as no symptoms are present
Immune-related rash	Grade 1 rash	Management with topical corticosteroid creams and/or oral antipruritic as clinically indicated.

Table 8: Recommended Treatment Modification for Nivolumab (Continued)

Immune-related AE	Severity	Treatment Modification
	Grade 2 rash	Continue therapy if involvement of < 30% of body surface area, are asymptomatic or toxicity can be managed with topical corticosteroid creams and antipruritics. If rash does not meet the above criteria, hold nivolumab and initiate treatment with topical corticosteroids. Consider systemic corticosteroids if rash does not improve to ≤ Grade 1 in ≤ 7 days.
	Grade 3 rash	Withhold dose until symptoms resolve and management with corticosteroids is complete
	Grade 4 rash	Permanently discontinue nivolumab

AE = adverse event; ALT = alanine aminotransferase; AST = aspartate aminotransferase.

Nivolumab should also be permanently discontinued for Grade 2 or 3 immune-related AEs that persist despite treatment modification or for inability to reduce corticosteroid dose to 10 mg prednisone or equivalent per day.

Consider resuming nivolumab only in subjects whose adverse reactions recover to ≤ Grade 1 or baseline.

Please refer to the nivolumab SmPC for updated details.

7.10.2. Nivolumab Dose Reductions

There will be no intra-subject dose reductions of nivolumab during the study.

7.10.3. Nivolumab Dose Interruption / Discontinuation

- Any Grade 2 drug-related uveitis or eye pain or blurred vision that does not respond to topical therapy and does not improve to Grade 1 severity within the re-treatment period (≤ 6 weeks and/or prior to next nivolumab dose) OR requires systemic treatment.
- Any dosing delay/interruption lasting > 6 weeks with the following exceptions: Dosing delays/interruptions to manage drug-related AEs such as prolonged steroid tapers are allowed. Prior to re-initiating treatment in the subjects with dosing delays/interruptions lasting > 6 weeks, the Celgene Medical Monitor must be consulted. Tumor assessments should continue as per protocol even if dosing is delayed/interrupted.
- Dosing delays/interruptions > 6 weeks that occur for non-drug-related reasons may be allowed if approved by the Celgene Medical Monitor. Prior to re-initiating treatment for the subjects with a dosing delay/interruption lasting > 6 weeks, the Celgene

Medical Monitor must be consulted. Tumor assessment should continue as per protocol even if dosing is delayed/interrupted.

- Any AE, laboratory abnormality or intercurrent illness which, in the judgment of the investigator, presents a substantial clinical risk to the subject with continued nivolumab dosing.

7.10.4. Management of Expected AEs While Receiving CC-122

7.10.4.1. Neutropenia, Thrombocytopenia, Anemia

Approximately 50% of subjects treated in Part B of CC-122-ST-001 experienced neutropenia (preliminary data). Neutropenia and febrile neutropenia should be managed with CC-122 dose interruption and G-CSF administration. Hematopoietic growth factors or other hematologic support, such as erythropoietin, darbepoetin, granulocyte-colony stimulating factor (G-CSF), GM-CSF, RBC- or platelet- transfusions are allowed in the study with therapeutic intent. Therapeutic use of G-CSF is allowed at any time for subjects experiencing Grade 4 neutropenia or any grade febrile neutropenia. Prophylactic use of granulocyte (or granulocyte-macrophage) growth factors is not allowed during Cycle 1.

7.10.4.2. Infection

In prior studies with CC-122 pyrexia and infections were observed in > 20% of subjects. Vigilance for the signs and symptoms of infection should be practiced and managed according to institutional standard medical practice. Routine infectious disease prophylaxis is not recommended; however, antibiotic, antiviral, antipneumocystis, antifungal, or other prophylaxis may be implemented during the study at the discretion of the investigator and/or SRC.

7.10.4.3. Pain

Tumor pain or treatment-induced pain can be controlled with opioid and opioid-related analgesics, such as codeine, meperidine, propoxyphene or morphine, administered at the clinician's discretion, and as dictated by medical need.

7.10.4.4. Dose Modification and Management of Cardiac Laboratory Abnormalities

Elevations of troponin-T or BNP warrant further investigation including assessment of the subject for signs and symptoms of cardiac injury, consideration of a cardiology consultation, and other cardiac evaluations (such as an exercise stress test, additional evaluation of LVEF, or other cardiac tests or cardioprotective medications recommended by a cardiologist), and the addition of cardioprotective therapy (eg, beta blockers or calcium channel blockers) as appropriate. Laboratory evaluation to assess for assay interference may also be warranted. For any confirmed elevation of troponin-T > ULN associated with significant elevation of BNP (20% increase from baseline and an absolute value > 100 pg/mL), CC-122 dosing should be held and the Sponsor should be notified. Additional cardiac monitoring should be performed as described in [Table 6](#) and as medically indicated. CC-122 may be restarted at a reduced dose or the same dose, in consultation with the Sponsor, based on troponin-T/BNP guidelines in [Table 6](#). For troponin-T elevations > ULN that either persist for > 7 days, recur with CC-122 rechallenge or are

associated with cardiac symptoms or significant changes in ECG or LVEF, CC-122 should be permanently discontinued.

In addition to routine ECG monitoring, please refer to the nivolumab SmPC for additional information regarding potential cardiac toxicity with nivolumab.

7.10.4.5. Dose Modification and Management of Pneumonitis

Pneumonitis has been observed in subjects taking CC-122. The diagnosis should be considered in subjects presenting with non-specific respiratory signs and symptoms such as hypoxia, pleural effusion, cough, dyspnea, or interstitial pulmonary infiltrates, and in whom infectious, neoplastic and other causes are excluded by appropriate investigations. Subjects should be specifically advised to report promptly any new or worsening respiratory symptoms they experience.

Those with radiological features suggestive of non-infectious pneumonitis but with minimal (Grade 1) symptoms may continue CC-122 without dose alteration. For drug-related Grade 2 pneumonitis, CC-122 and nivolumab treatment should be interrupted and corticosteroids may be indicated. Once symptoms have resolved to Grade 0 or 1, CC-122 may be reintroduced at the next lower dose level. For drug-related Grades 3 or 4 pneumonitis, CC-122 and nivolumab must be permanently discontinued and corticosteroids are recommended until clinical symptoms have resolved.

Pneumonitis has been also observed in subjects taking nivolumab. Pneumonitis may be considered related to both IPs. Please refer to nivolumab SmPC (or Appendix H in Section 18.8) for pneumonitis management guidelines in subjects receiving nivolumab.

7.10.4.6. Dose Modification and Management of Tumor Flare Reaction

Subjects in this study should be monitored for tumor flare. Tumor flare reaction (TFR) is defined as a sudden and tender increase in the size of the disease-bearing sites, including the lymph nodes, spleen and/or the liver, often accompanied by low-grade fever, and non-pruritic diffuse rash. Tumor flare usually occurs within the first cycle of treatment. Tumor flare reaction may mimic progression of disease; however, the TFR will generally subside over time. Therefore, careful monitoring and evaluation is important prior to discontinuing a study subject for PD in the initial cycles of CC-122 therapy.

There are currently no laboratory or radiological tests that distinguish TFR from PD. The distinction should be made on clinical grounds, incorporating observations such as associated physical findings, laboratory findings, and pace of disease before and after institution of treatment. Tumor flare will be recorded as an AE (graded using the NCI CTCAE version 3.0 criteria) and not as PD.

Treatment of the TFR is up to the discretion of the investigator depending on the severity and clinical situation. In mild to moderate cases (Grades 1 to 2), it is suggested that CC-122 be continued along with symptomatic treatment such as nonsteroidal anti-inflammatory drugs (NSAIDs) and/or narcotics. Corticosteroids can be administered at the investigator's discretion. In more severe cases (Grade 3 to 4), CC-122 and/or nivolumab should be interrupted and therapy with corticosteroids should be initiated. NSAIDs and/or narcotics may also be used at the investigator's discretion. When symptoms resolve to \leq Grade 1, CC-122 and/or nivolumab can be restarted at the same dose level.

7.10.4.7. Management and Follow-up of Liver Function Test Abnormalities Grade 3

Subjects experiencing a Grade 3 liver function test (LFT) elevation should undergo the additional testing below until LFT abnormalities improve to Grade 1 or better:

- Hepatitis A, B, and C acute infection serology testing
- Once weekly HBV viral load (for subjects with known HBV infection)
- Twice weekly check of AST, ALT, bilirubin, alkaline phosphatase, PT, PTT, INR

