6.5.2. Treatment Beyond Progression

Subjects will be permitted to continue treatment beyond initial RECIST 1.1 defined progressive disease as long as they meet the following criteria:

- Continue to meet all other study protocol eligibility criteria
- Investigator assessed clinical benefit and do not have rapid disease progression or clinical deterioration
- Stable performance status
- Tolerance to IP
- Other treatment options, including no treatment and supportive care, have been discussed and subject has consented to continue IP

A follow-up scan should be performed within 4 to 6 weeks of the original PD to determine whether there has been a decrease in the tumor size, or continued PD. Thereafter, response assessment should occur per standard of care. The assessment of clinical benefit should be balanced by clinical judgment as to whether the subject is clinically deteriorating and unlikely to receive any benefit from continued treatment. If the Investigator feels that the subject continues to achieve clinical benefit by continuing treatment, the subject may remain on study treatment. The decision to continue treatment should be discussed with the Celgene Medical Monitor and documented in the study source documents.

Study therapy should be discontinued if further progression is documented. For the subjects who continue study therapy beyond progression, further progression is defined as an additional 10% increase in tumor burden from time of initial PD. This increase in tumor burden includes an increase in all target lesions and/or the development of new measurable lesions.

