4.2. Study Endpoints

Table 2: Study Endpoints

Endpoint	Name	Description	Timeframe
Primary Phase 1	The incidence of DLTs and the incidence and severity of treatment-emergent adverse events (TEAEs)	See Section 7.6 of protocol for the definition of DLTs	Dose Escalation Phase
Primary Phase 2	Preliminary efficacy as measured by ORR	The combined incidence of CR + PR, by investigator assessment of response by RECIST 1.1	Dose Escalation and Dose expansion Phase
Secondary	Preliminary efficacy	Disease control rate (DCR), duration of response (DoR), progression free survival (PFS), overall survival (OS), and time to progression (TTP) based on investigator assessment of response using RECIST 1.1 guidelines	Dose Escalation and Dose expansion Phase
Secondary	Plasma PK parameters	Including but not limited to maximum observed concentration (C_{max}), area under the concentration time curve (AUC), time to maximum concentration (T_{max}), terminal half-life ($t_{1/2}$), apparent total body clearance (CL/F) and apparent volume of distribution (V_z/F) for CC-122 and Nivolumab after multiple dose administration	Dose Escalation Phase
[REDACTED]	[REDACTED]	[REDACTED]	[REDACTED]
[REDACTED]	[REDACTED]	[REDACTED]	[REDACTED]
[REDACTED]	[REDACTED]	[REDACTED]	[REDACTED]

Endpoint	Name	Description	Timeframe
[REDACTED]	[REDACTED]		[REDACTED]

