10.1. Response Criteria

Investigators will use RECIST 1.1 and irRECIST to assess tumor response for subjects treated with CC-122 in combination with Nivolumab (see Table 4).

Table 4: Time Point Overall Tumor Response Definitions by RECIST 1.1 and irRECIST

Overall Response RECIST 1.1	RECIST 1.1 ^[1]	Overall Response irRECIST	irRECIST ^[2]
CR	Disappearance of all target lesions, disappearance of all non-target lesions and normalisation of tumor marker level. All lymph nodes must be non-pathological in size (<10mm short axis).	irCR	Complete disappearance of all measurable and non-measurable lesions. Lymph nodes must decrease to < 10 mm in short axis. Confirmation of response is not mandatory.
PR	At least a 30% decrease in the sum of diameters of target lesions, taking as reference the baseline sum diameters, no unequivocal progression of non-target lesions and no new lesion(s), but the criteria for CR are not met	irPR	Decrease of $\geq 30\%$ in TMTB relative to baseline, non-target lesions are irNN, and no unequivocal progression of new non-measurable lesions.
SD	Neither sufficient shrinkage in the sum of diameters of target lesions to qualify for PR nor sufficient increase to qualify for PD, taking as reference the smallest sum diameters while on study, no unequivocal progression of non-target lesions and no new lesion(s).	irSD	Failure to meet criteria for irCR or irPR in the absence of irPD.
PD	At least a 20% increase in the sum of diameters of target lesions from nadir. In addition, the sum must also demonstrate an absolute increase of at least 5 mm, or unequivocal progression of non-target lesions, or appearance of new lesion(s).	irPD	At least 20% increase and minimum 5 mm absolute increase in TMTB compared to nadir, or irPD for non-target or new non-measurable lesions. Confirmation of progression is recommended minimum 4 weeks after the first irPD assessment.

Abbreviations: CR = Complete Response; PR = Partial Response; SD = Stable Disease; PD = Progressive Disease; ir=immune-related; irNN = irNon-CR/Non-PD, TMTB = total measured tumor burden,

^[1] RECIST 1.1 overall response is based on the sum of diameters of the target lesions.

^[2] irRECIST overall response is based on TMTB for target and new measurable lesions.

Table 5: RECIST 1.1 Best Overall Response When Confirmation of CR and PR is Required

Overall Response First Time Point	Overall Response Subsequent Time Point	Best Overall Response
CR	CR	CR
CR	PR	SD, PD or PR ^[1]

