CR	SD	SD provided minimum criteria for SD duration met, otherwise, PD
CR	PD	SD provided minimum criteria for SD duration met, otherwise, PD
CR	NE	SD provided minimum criteria for SD duration met, otherwise NE
PR	CR	PR
PR	PR	PR
PR	SD	SD
PR	PD	SD provided minimum criteria for SD duration met, otherwise, PD
PR	NE	SD provided minimum criteria for SD duration met, otherwise NE
NE	NE	NE

Abbreviations: CR = complete response, PR = partial response, SD = stable disease, PD = progressive disease, NE = non evaluable.

[1] If a CR is truly met at first time point, then any disease seen at a subsequent time point, even disease meeting PR criteria relative to baseline, makes the disease PD at that point (since disease must have reappeared after CR). Best response would depend on whether minimum duration for SD was met. However, sometimes 'CR' may be claimed when subsequent scans suggest small lesions were likely still present and in fact the subject had PR, not CR at the first time point. Under these circumstances, the original CR should be changed to PR and the best response is PR.

Note: All responses after first PD will not be considered as a response.

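### The tumor-flare rule can keep a scan that meets RECIST 1.1 progression out of the investigator-assessed endpoints, and neither document says how such a scan is coded

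*Protocol*

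**What the plan says.** **Flare rule.** Protocol 7.10.4.6 describes flare as sudden, tender growth at disease sites, the liver among them, that can look like progression. It states: "There are currently no laboratory or radiological tests that distinguish TFR from PD". It then says: "The distinction should be made on clinical grounds, incorporating observations such as associated physical findings, laboratory findings, and pace of disease". The recording instruction is: "Tumor flare will be recorded as an AE (graded using the NCI CTCAE version 3.0 criteria) and not as PD". On timing: "Tumor flare usually occurs within the first cycle of treatment". The section also asks for care before a subject is discontinued for progression in the initial cycles.

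**Endpoint rules.** SAP Section 4.2 defines the Phase 2 primary endpoint as "The combined incidence of CR + PR, by investigator assessment of response by RECIST 1.1", and bases DCR, PFS and TTP on the same investigator reading. SAP Table 4 gives the target-lesion part of progression as "At least a 20% increase in the sum of diameters of target lesions from nadir", with an absolute increase of at least 5 mm. The alternatives are unequivocal non-target progression or a new lesion. Table 5 adds: "Note: All responses after first PD will not be considered as a response". SAP Section 10.2 ends the window for best overall response (BOR) at progression. None of these rules, nor the PFS censoring table (Table 8), mentions flare.

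**Existing route for apparent progression.** Protocol 6.5.2 begins: "Subjects will be permitted to continue treatment beyond initial RECIST 1.1 defined progressive disease". It sets conditions and a rescan at 4 to 6 weeks. Protocol 6.5.4 starts irRECIST, as an exploratory reading, once RECIST 1.1 progression has been documented and treatment continues.

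**The concern.** Two rules can apply to the same scan and give different answers. Under SAP Table 4, growth of 20% and 5 mm from nadir is progression. Under Protocol 7.10.4.6, the same growth judged to be flare is not recorded as progression. The person choosing is the unblinded investigator, and the protocol concedes that no test can check the choice.

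The safeguards for atypical response do not catch this case. The 6.5.2 conditions, the rescan and irRECIST all start from documented RECIST progression. A scan labelled flare does not trigger them, and it does not trigger the Table 5 bar on later responses either. Independent review is optional under Protocol 6.5. No section available for this review says whether a flare-labelled scan enters as PD, SD or NE, asks for a confirming scan, or plans a sensitivity analysis. With no comparator arm, nothing offsets a shift in one direction.

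**Working it through.** The plan states no figure for this point. The check covers direction, timing and weight per subject.

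**1. Direction, endpoint by endpoint, when progression is withheld at one scan**
- PFS and TTP: the event moves to a later date or becomes a censoring. Both estimates lengthen.
- DCR: improves only if the subject then qualifies as SD or better. Protocol 6.5.1 requires an assessment at least 6 weeks (42 days) from Cycle 1 Day 1 for SD.
- ORR: improves only if a CR or PR is later recorded that the Table 5 note would have excluded.
- BOR: a subject who already had PR, or SD of sufficient length, before the scan gains nothing unless a better response follows.

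**2. Timing at the Week 8 scan** (Protocol 6.5: every 8 weeks, ±7 days)
- First scan: 8 × 7 = day 56, window day 49 to 63.
- Next scan: 16 × 7 = day 112, window day 105 to 119.
- Nominal delay: 112 − 56 = 56 days. Shortest: 105 − 63 = 42. Longest: 119 − 49 = 70.
- SAP 10.5.1 reports PFS at 90 days. Since 63 < 90 < 105, the subject moves from event to event-free at that landmark for any timing within the windows, unless an unscheduled scan or death intervenes.

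**3. Timing at an unscheduled Cycle 1 scan** (allowed when clinically indicated)
- From day 28 to the nominal Week 8 scan is 56 − 28 = 28 days.
- Day 56 is still before day 90, so 3-month PFS does not change if progression is called then.
- A day-28 reading is before day 42, so it cannot support SD as BOR.

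**4. Weight of one subject**
- About 20 escalation subjects (Protocol 4.1): 1/20 = 5 points.
- A dose cohort of 6: 1/6 = 16.7 points.
- These apply to 3-month PFS (ignoring censoring) and to DCR, and to ORR only when a later response is recorded.
- For scale, the Clopper-Pearson 95% interval is 5.7% to 43.7% for 4/20 and 8.7% to 49.1% for 5/20. One subject is small against that uncertainty.

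**5. Possible size for ORR (assumptions, not document figures)**
- Let the true ORR be 20%, let q be the share of non-responders with a progression scan called flare, and let r be the share of those later counted as CR or PR.
- Apparent ORR = 0.20 + 0.80 × q × r.
- Low case, q = 2%, r = 10%: 0.20 + 0.0016 = 20.2%.
- High case, q = 10%, r = 50%: 0.20 + 0.04 = 24.0%.
- At n = 20 the high case is 0.04 × 20 = 0.8 of a subject.

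**The case against.** The best defence is that 7.10.4.6 is an adverse-event section. It describes a clinical syndrome, often with low-grade fever and rash, and its stated worry is premature discontinuation. On that reading Table 4 alone governs the time-point response, and the flare text governs only the AE form. This does not fit the recording sentence, which goes beyond the AE form and says what the event is not to be recorded as. Some investigators may still read it that way, and the plan should not leave the coding to each reader.

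Several limits do stand:
- Flare is said to occur mostly in the first 28 days, and the earliest scheduled scan is day 49. Overlap therefore comes mainly from unscheduled scans or from late or persistent flare.
- Protocol 6.5.1 refers to Appendix B (Section 18.2) for response details. It was not in the text available for this review, and a flare rule there cannot be excluded.
- Recording progression has consequences for conduct. It brings the 6.5.2 conditions into play, and scheduled scanning under Protocol 6.5 runs only until radiologic progression.

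A reader might also infer that every relabelled subject improves BOR, or that the delay is always at least 8 weeks. Steps 1 to 3 show neither is so. A reader might point to the Phase 2 benchmark: 10/30 gives a Wilson interval of 19.2% to 51.2%, which includes 20%, and 11/30 gives 21.9% to 54.5%, which does not. However, SAP Section 15 cancels the expansion and drops the futility analysis, so that decision will not be made.

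**Conclusion.** The conflict is real. Followed as written, Protocol 7.10.4.6 allows a scan meeting RECIST 1.1 progression to be kept out of PFS, TTP, DCR and sometimes ORR, and for these endpoints the effect is nil or favourable. PFS and TTP are the most directly exposed: a Week 8 progression would move by 42 to 70 days and cross the 90-day landmark. DCR and ORR move only under the further conditions in step 1.

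The total size is unknown, because the documents give no rate of flare or of relabelling. What remains exposed is descriptive efficacy in up to about 20 escalation subjects, where one subject is 5 points overall and up to about 17 points in a cohort of six. The documents do not support saying that the results are inflated, only that the plan permits it and has no check. The conclusion assumes that Appendix B contains no rule settling the matter.

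**What to change.** 1. Reconcile Protocol 7.10.4.6 with Protocol 6.5.2 and 6.5.4, SAP Tables 4 and 5, and Protocol Appendix B.
2. State in SAP 10.1 that the RECIST 1.1 time-point response follows the scan measurements and lesion findings regardless of any flare AE, with flare recorded in addition as an AE.
3. At minimum, add a sensitivity analysis of BOR, ORR, DCR, PFS and TTP that counts flare-labelled scans meeting the progression criteria as PD on the scan date.

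This concerns endpoint recording only. No treatment or continuation rule is proposed, and how a flare call relates to the 6.5.2 conditions is for the sponsor to settle when reconciling the sections.

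**Cost.** One recording sentence in the SAP, an aligned sentence in the protocol, and one sensitivity table. SAP Section 10 already lists change from nadir and non-target findings, so the analysis mainly needs a link from the scan to the flare AE. The downside is that RECIST-based PFS, TTP, DCR and possibly ORR may look slightly less favourable, and a true flare would count as progression under RECIST 1.1. The sensitivity analysis alone avoids changing the primary reading, but leaves the contradiction in the protocol.
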